8.2.1. Inclusion criteria

Patients must meet all of the following inclusion criteria to be eligible for inclusion in the study:

1. Unique enrollees in the HealthVerity Vaccine dataset any time **after** 10 December 2020
2. At least 12 years on the index date (ie, first vaccination date)
3. No evidence of prior COVID-19 infection (a medical claim, pharmacy claim, or chargemaster record with an International Classification of Diseases, 10th Revision, Clinical Modification (ICD-10-CM) diagnosis code of U07.1) in the 12 months prior to the index date
4. Have 12 months of continuous enrollment with medical benefits (with or without pharmacy benefits) prior to the index date

Subjects with an IC condition were identified via an algorithm originally developed and validated by Greenberg et al²⁴ for use in administrative claims database studies. For this study, this algorithm will be modified and expanded based on expert medical opinion. The algorithm is depicted in [Figure 1](#).

Subjects will be identified as immunocompromised if they had ≥ 1 hospitalization or ≥ 2 outpatient visits on separate dates with an ICD-10-CM code on a healthcare claim indicating an IC condition or if they had usage of specific immunosuppressive medications during the 12-month baseline period. The IC case definition will incorporate 8 groups based on clinical diagnoses only, 1 group based on both clinical diagnoses and usage of immunosuppressive medication, and 2 other groups based on usage of immunosuppressive medication only, for a total of 11 groups with an IC condition ([Figure 1](#)). Subjects with >1 IC condition will also be assessed, for a total of 12 mutually exclusive groups for inclusion in this study. The list of ICD-10-CM codes used to identify IC cases by diagnosis and list of immunosuppressive medications are shown in the Annex.

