Eight of the disease groups will include subjects with 1) symptomatic human immunodeficiency virus (HIV)/acquired immunodeficiency syndrome (AIDS); 2) solid malignancy; 3) bone marrow transplant; 4) organ transplant (excluding bone marrow); 5) rheumatologic or other inflammatory condition; 6) a primary immunodeficiency; 7) other immune conditions; and 8) chronic kidney disease (CKD) or end stage renal disease (ESRD). Subjects in these IC groups (shown as “Group 1” in [Figure 1](#)) will be further stratified by treatment status: those with usage of immunosuppressive medications for >14 days anytime during the baseline period and those without any evidence of >14 days of usage of an immunosuppressive medication during the baseline period. Subjects with a bone marrow or

organ transplant will be further stratified by those who received their 1st vaccine dose >100 days prior to their transplant and those who received it <100 days prior to their transplant. Subjects with a solid malignancy will be further stratified by their treatment type: chemotherapy or radiation therapy or immunomodulator, or a mix of these treatments.

The 9th subject group (shown as “Group 2” in [Figure 1](#)) will include those with a hematologic malignancy, required to have usage of an immunosuppressive medication (chemotherapeutic agent, immunomodulator, or systemic corticosteroid) for >14 days anytime during the baseline period; this subject group will be further stratified by their use of an immunosuppressive medication >6 months or ≤ 6 months prior to their index date.

The 10th subject group will include subjects with usage of an immunosuppressive medication (chemotherapeutic agent, immunomodulator, or systemic corticosteroid excluding low-dose [<60mg/day] prednisone) for >14 days anytime during the baseline period, but without any ICD-10-CM diagnosis codes indicating the above listed IC conditions on a healthcare claim anytime during the baseline period. Subjects with >14 days usage of antimetabolites anytime during the baseline period will be excluded from this subject group and placed in the 11th subject group.

[figure not shown]

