This algorithm differs from that used in Greenberg et al²⁶ by the following modifications, considered relevant for COVID-19 based on expert medical opinion: the inclusion of subjects with a solid malignancy who had radiation therapy or any treatment mix; the separation of subjects with a bone marrow transplant and those with an organ transplant; the inclusion of chronic inflammatory demyelinating polyneuropathy and immune thrombocytopenic purpura in the “rheumatologic or other inflammatory condition” group; the inclusion of sickle cell disease, asplenia, and psoriatic arthritis in the “other immune disorders” group; the addition of subjects with primary immunodeficiencies and those with CKD or ESRD; the requirement that subjects with a hematologic malignancy have evidence of usage of an immunosuppressive medication; the reclassification of subjects with only usage of an immunosuppressive medication; the removal of subjects with usage of only low dose prednisone; and the inclusion of an ad-hoc group of subjects who had taken anti-metabolites. Additionally, the following subcategories will be created: the first 9 subject groups were stratified according to treatment status; organ transplant subjects will be stratified according to time of receipt of the first COVID-19 vaccine dose in relation to the date of transplant; and subjects with hematologic malignancy will be stratified by time of receipt of treatment relative to their 1st vaccine dose.

When categorizing subjects with the different types of IC conditions, all the subject groups will be mutually exclusive. Subjects meeting the criteria for classification into only a single IC group will be classified accordingly into subject groups 1-11. Any subjects meeting the criteria for classification into multiple IC groups will be categorized into the >1 IC condition group (12th subject group).

All subjects will be grouped into an overall study population consisting of subjects identified as having an IC condition or not (i.e., non-IC). Subjects with an IC condition will be further categorized into the specific IC condition groups.

Figure 1: Algorithm to define immunocompromising conditions

Algorithm for case definitions of IC conditions in HealthVerity US claims database

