ANNEX 3. ICD-10 CODE LIST

IC Condition	ICD-10 Code
HIV/AIDS*	B20-B24
Solid malignancy	
Organ/system malignant tumors	C00-C07; C11-C19; C22-C80; Z85
Neuroendocrine tumors	C7A; C7B; D3A
Neoplasms of uncertain behavior	D00-D49
Bone marrow transplant	Z94.81
Organ transplant	
Complications of transplanted organ	T86
Organ transplant status	Z94 except Z94.81; Z98.85
Rheumatologic or other inflammatory condition	
Sarcoidosis	D86
Amyloidosis Not Otherwise Specified (NOS)	E85
Familial Mediterranean fever	E85.0; M04
Amyloidosis Not Elsewhere Classified (NEC)	E85.1; E85.3; E85.8
Multiple sclerosis	G35
Other Central Nervous System (CNS) demyelination	G36; G37.1; G37.3; G37.8; G37.9
Acute infective polyneuritis	G61.0; G61.9
Acute myocarditis	I40
Polyarteritis nodosa and other	M30
Allergic alveolitis/pneumonitis NOS	T78.40; J67.9
Other alveolar pneumonopathy	J84.01; J84.02; J84.09

PFIZER CONFIDENTIAL

IC Condition	ICD-10 Code
Enteritis and colitis	K50-K52
Lupus erythematosus	L93.0; L93.2; M32
Diffuse connective tissue disease	L94; M35.8; M35.9
Arthropathy with infection	M12.9; M01.X0; M02.10
Crystal arthropathies	M11
Rheumatoid arthritis/inflammatory polyarthropathy	M05-M14
Inflammatory spondylopathies	M46
Polymyalgia rheumatica	M31.5; M35.3
Chronic inflammatory demyelinating polyneuropathy	G61.81
Immune thrombocytopenic purpura	D69.3
Primary Immunodeficiency	
X-linked agammaglobulinemia	D80.8
Common variable immunodeficiency	D83.1; D83.2; D83.8; D83.9
Immunoglobulin A (IgA) deficiency	D80.2
Immunoglobulin G (IgG) sub-class deficiency	D80.3
Severe combined immunodeficiency	D81.1
Di George syndrome	D82.1
Wiskott-Aldrich	D82.0
Ataxia telangiectasia	G11.3
Interferon-gamma/Interleukin 12 axis deficiencies	D84.89
Persistent complement, properdin or Factor B deficiency	D84.1
Received eculizumab for >14 days in the baseline period	
Chronic granulomatous disease	D71
Chediak-Higashi	E70.330
Leukocyte adhesion deficiency	D72: Genetic anomalies of leukocytes
Myeloperoxidase deficiency	D72.89: Other specific disorders of White Blood Cells (WBCs)

PFIZER CONFIDENTIAL

IC Condition	ICD-10 Code
Other immune conditions	
Disorders of immune mechanism	D89
Neutropenia	D70
Functional disorders of neutrophils	D71
Genetic anomalies of leukocytes	D72.0
Decreased leukocyte count	D72.81
Leukocyte disease NEC	D72.89
Leukocyte disease NOS	D72.9
Myelofibrosis	D75.81
Blood diseases NEC	D47.4; D75.89; D75.9; D89.2
Blood diseases NOS	D75.9; D75.89
Immunologic findings NEC	R76; R83.4-R87.4; R89.4

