Nonspecific immune findings NEC and NOS	R76; R83.4-R87.4; R89.4
Sickle cell disease	D57
Asplenia	Q89.01
Psoriatic arthritis	L40.52
Kidney condition	
Chronic kidney disease	A18.11; A52.75; B52.0; C64.x; C68.9; D30.0x; D41.0x-D41.2x; D59.3; E08.2x; E09.2x; E10.2x; E10.65; E11.2x; E11.65; E13.2x; E74.8; I12.xx; I13.0; I13.1x; I13.2; K76.7; M10.3x; M32.14; M32.15; N01.x-N08.x; N13.1; N13.1x-N13.39; N14.x; N15.0; N15.8; N15.9; N16; N17.x; N18.1-N18.5; N18.8; N18.9; N19; N25.xx; N26.1; N26.9; O10.4xx; O12.xx; O26.83x; O90.89; Q61.02; Q61.1x-Q61.8; Q26.0-Q26.39; R94.4
End stage renal disease	N18.6 AND on dialysis (any type): Z99.2; Z49; Z9115; Z4931; OR Z4901
On hemodialysis	Any subject with the ESRD codes above and ≥ 1 hemodialysis procedure session during the baseline period identified by at ≥ 1 of the following codes: Z49.31;

IC Condition	ICD-10 Code
	Z49.32; I953; A4680; A4690; A4706- A4709; A4730; A4740; A4750; A4755; A4802; A4870; A4890; A4918; E1520; E1530; E1540; E1550; E1560; E1575; E1580; E1590; E1600; E1610; E1615; E1620; E1625; E1636; G0365; G0392; G0393; G8081; G8082; G8085; S9335; 90935; 90937; 90940; 93990; 36800; 36810; 36815
On peritoneal dialysis	Any subject with the ESRD codes above and ≥ 1 peritoneal dialysis procedure session during the baseline period identified by ≥ 1 of the following codes: Z49.02; 90945; 90947
Hematologic malignancy**	
Lymphatic and hematopoietic tissue malignancy	C81-C83; C88-C96

CNS: central nervous system; ICD-10: International Classification of Diseases, 10th Revision; IgG: Immunoglobulin G, IgA: Immunoglobulin A, NOS: not otherwise specified; NEC: necrotizing enterocolitis; WBCs: White blood cells.

*Excluded asymptomatic HIV code of ICD-10: Z21.

**Required to have usage of an immunosuppressive medication (chemotherapeutic agent, immunomodulator, or systemic corticosteroids) for >14 days anytime during the baseline period.

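### Annex 3 lets nonspecific immune findings, and an unrestricted sickle-cell category, qualify subjects as immunocompromised on diagnosis codes alone

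*Combined protocol and SAP*

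**What the plan says.** Annex 3 lists two rows under Other immune conditions with the same codes: "Immunologic findings NEC R76; R83.4-R87.4; R89.4" and "Nonspecific immune findings NEC and NOS R76; R83.4-R87.4; R89.4". The same group has the row "Sickle cell disease D57", with no exception. Section 8.2.1 describes the intended addition as "the inclusion of sickle cell disease, asplenia, and psoriatic arthritis".

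Section 8.2.1 makes this the seventh of eight groups defined by diagnosis only. The entry rule is "≥ 1 hospitalization or ≥ 2 outpatient visits on separate dates with an ICD-10-CM code on a healthcare claim indicating an IC condition", within the 12-month baseline. Immunosuppressive treatment is not needed for entry. It only divides these groups into treated subjects and "those without any evidence of >14 days of usage of an immunosuppressive medication during the baseline period".

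Elsewhere the annex does narrow its codes. The HIV footnote reads "Excluded asymptomatic HIV code of ICD-10: Z21", and the organ transplant row is written as "Z94 except Z94.81".

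Section 8.2.1 also makes the groups mutually exclusive: a subject who meets the criteria for several groups goes into a twelfth group for more than one IC condition. Section 8.7 reports each group separately, pools them into the IC cohort, and compares IC with non-IC.

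**The concern.** The study is meant to show which IC conditions go with weaker vaccine protection (Section 6). By the plan's own labels, the R76, R83.4-R87.4 and R89.4 rows hold findings, some of them nonspecific, and not named diseases. Table 1 calls the same group intrinsic immune conditions, so label and content do not match. For D57, the row label and Section 8.2.1 both say disease, but the code entry is a whole category.

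Subjects with normal immune function who enter this way would make group 7 look better protected than people with real immune disease are. They would also pull the pooled IC versus non-IC contrast toward no difference. A second effect reaches other groups: a rheumatologic patient with two outpatient visits carrying an R76 code leaves the rheumatologic group for the twelfth group, although nothing beyond a finding was added.

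**Working it through.** The plan states no figure on this point, so there is none to reproduce. The check has two parts.

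**Tracing a subject through the rules**

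1. A subject has two outpatient visits on separate dates in the baseline year, each coded R76, with no other listed code and no immunosuppressive drug.
2. R76 is in Annex 3 under Other immune conditions, so the entry rule in Section 8.2.1 is met.
3. No treatment is required. The subject enters group 7, untreated stratum, and hence the pooled IC cohort.
4. If the subject also meets the criteria for another group, the exclusivity rule moves them to the twelfth group.
5. A single outpatient claim does not qualify.
6. The duplicate R76 row is redundant and changes nobody's classification.

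**Size of the dilution**

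Inputs, all assumed because the documents give no counts:

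- f, the share of group-7 person-time from subjects who in fact have the non-IC rate
- RR, the true rate ratio against non-IC for the rest of group 7
- a true vaccine effectiveness (VE) of 70% for real group-7 disease and 90% for non-IC, with equal coverage and equal unvaccinated risk in both parts

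Formulas:

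- observed ratio = (1 − f) × RR + f = 1 + (RR − 1)(1 − f)
- observed rate difference = (1 − f) × true difference
- observed VE = (1 − f) × 70% + f × 90%

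| f | observed ratio, true RR 3 | observed ratio, true RR 2 | observed VE, true 70% |
|---|---|---|---|
| 5% | 2.90 | 1.95 | 71% |
| 10% | 2.80 | 1.90 | 72% |
| 20% | 2.60 | 1.80 | 74% |
| 30% | 2.40 | 1.70 | 76% |
| 50% | 2.00 | 1.50 | 80% |
| 70% | 1.60 | 1.30 | 84% |

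Example: RR = 3 and f = 0.30 give 1 + 2 × 0.70 = 2.4.

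For the pooled IC cohort, the relevant share is group 7's weight w times f. With w = 10% and f = 50%, the pooled share is 5%, and a true pooled ratio of 3 reads 1 + 2 × 0.95 = 2.9. With w = 30% and f = 50%, the share is 15%, and the ratio reads 1 + 2 × 0.85 = 2.7.

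**The case against.** Several points on the other side are fair.

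- **The effect may be small.** At f of 5% to 10%, a ratio of 3 falls only to 2.9 or 2.8, and group 7 is one of twelve pooled groups. This stands: the size is unknown until the subjects are counted.
- **The direction is conditional.** The arithmetic assumes that these subjects have the non-IC rate. If their exposure differs, their rate may differ too. This also stands.
- **The plan partly covers the problem.** Section 8.9 says the effect of the modifications on the algorithm's accuracy cannot be assessed, Section 8.7 allows sensitivity analyses on the IC case definition, and the treatment strata would separate untreated subjects. But none of these names the codes. The untreated stratum also mixes subjects with real disease and subjects with findings only. The specificity of 97.6% in Section 8.9 belongs to the source algorithm, validated, by its title in the reference list, in patients with severe sepsis; sickle cell disease was added afterwards.
- **The findings rows may be inherited.** Section 8.2.1 itemises the departures from the source algorithm, and these rows are not among them. Removing them would be one more departure. This is a reason to keep the current list visible in a parallel analysis.

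A reader who knows ICD-10-CM might infer more: that R76 brings in positive tuberculosis tests and D57 brings in sickle-cell trait, so that healthy carriers and people who were merely screened become IC. The documents do not support that as stated. They print no sub-codes for either category, so the contents need a code-book check. They say nothing about how common such subjects are or how they respond to vaccination. And one isolated outpatient result is not enough to qualify.

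**Conclusion.** The concern holds as a mismatch between codes and labels. As written, the plan lets subjects whose only qualifying codes are nonspecific findings into group 7 and the pooled IC cohort, and lets those codes shift subjects from other groups into the twelfth. That part rests on the plan's own labels and rules. The D57 part is weaker: the entry is broader in form than the stated intent, but whether it admits a carrier state must be confirmed in the code book.

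The size cannot be settled from the documents. On the assumptions above, a true group-7 ratio of 3 would be seen as anything from 2.9 to 1.6, and the pooled ratio would move less. The bias is toward no IC versus non-IC difference only if the misplaced subjects have roughly the non-IC rate. This is a cheap improvement worth making before the analysis, and not a flaw that invalidates the study.

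**What to change.** 1. Check D57 in the ICD-10-CM code book and list only the sub-codes that denote disease, so that any carrier-state code is excluded, in the same way as the HIV footnote already removes the asymptomatic code.
2. Do not let R76, R83.4-R87.4 or R89.4 qualify a subject on their own. If the sponsor prefers to keep the current list as the main definition, pre-specify by name, under the IC case definition analyses in Section 8.7, an analysis that removes these codes, and report both side by side.
3. Report how many subjects qualify for IC only through these codes, and how many are in the twelfth group only because of them. This replaces the assumed f with a count of the subjects at issue.
4. Delete the duplicate row.

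The cost is a code-list edit and a rerun on data already held. Group 7 becomes smaller and its interval wider, and the algorithm departs once more from its source.
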